7.7.1 Dosing Delays/Dose Modifications

Dose will be modified according to creatinine clearance; see Section 7.7 for further details.

Dose will be delayed or stopped if clinically significant major or non-major bleeding occurs.

7.8 General Concomitant Medication and Supportive Care Guidelines

All concomitant medications will be recorded and/or updated on subject medication log throughout the course of the study and saved in subject binder, if applicable.

Subjects enrolled on this study are permitted to receive other agents for treatment of their COVID-19 disease, including, but not limited to, remdesivir, eculizumab, tocilizumab, anakinra, and hydroxychloroquine. Co-enrollment on investigational trials for the treatment of COVID-19 is permitted.

7.9 Duration of Therapy and Criteria for Removal from Study

In the absence of treatment delays due to adverse event(s), treatment may continue for 28 days or until one of the following criteria applies:

- Intercurrent illness that prevents further administration of treatment,
- Unacceptable adverse event(s),
- Subject decides to withdraw from the study, or
- General or specific changes in the subject's condition render the subject unacceptable for further treatment in the judgment of the investigator.

In the event of hospital discharge, the decision to continue or discontinue anticoagulation therapy will follow institutional guidelines regarding anticoagulation at the time of hospital discharge (Appendix C). Anticoagulation treatment may continue beyond Day 28 if the investigator and/or treating physician considers it appropriate for the patient's clinical care.

Subjects may discontinue therapy if any of the following events occur:

- Major bleeding, defined (as per ISTH guidelines) as acute clinically overt bleeding associated with one or more of the following:
 - A decrease in hemoglobin of 2 g/dL or more;
 - A transfusion of 2 or more units of packed red blood cells;
 - Bleeding that occurs in at least one of the following critical sites:
 - Intracranial
 - Intra-spinal
 - Intraocular (within the corpus of the eye; thus, a conjunctival bleed is not an intraocular bleed)
 - Pericardial
 - Intra-articular
 - Intramuscular with compartment syndrome
 - Retroperitoneal
 - Bleeding that necessitates surgical intervention
- Clinically relevant non-major bleeding event defined as acute clinically overt bleeding that does not meet the criteria for major and consists of:
 - Any bleeding compromising hemodynamics;
 - Spontaneous hematoma larger than 25 cm², or 100 cm² if there was a traumatic cause;
 - Intramuscular hematoma documented by ultrasonography
 - Epistaxis or gingival bleeding requiring tamponade or other medical intervention or bleeding from venipuncture for >5 minutes
 - Hemoptysis, hematemesis or spontaneous rectal bleeding requiring endoscopy or other medical intervention;
 - Clinically relevant bleeding defined as the composite of major and clinically relevant non-major bleeding

7.10 Duration of Follow Up

Subjects will be followed for 6 months after discharge from hospital with the intention to get complete follow-up, or a minimum of vital status and the occurrence of recurrent deep venous thrombosis, pulmonary embolism, or major bleeding.

7.11 Measures to Minimize Bias: Randomization

Blocked randomization will be performed in the study. A series of blocks with random block sizes will be generated with a 1:1 allocation ratio to allow for an equal number of

patients in the intermediate dose prophylaxis arm and therapeutic anticoagulation treatment arm. Patients will not be stratified. The block randomization scheme will be provided by a biostatistician not directly involved in the analysis of the study and uploaded to the REDCap randomization module. Randomized assignments will be generated in REDCap after all eligibility criteria have been met. Blinding is not relevant as the study is open-label.

8. Study Intervention Discontinuation and Participant Discontinuation/Withdrawal

8.1 Discontinuation of Study Intervention

Discontinuation from study intervention does not mean discontinuation from the study, and remaining study procedures should be completed as indicated by the study protocol. If a clinically significant finding is identified (including, but not limited to changes from baseline) after enrollment, the investigator or qualified designee will determine if any change in participant management is needed. Any new clinically relevant finding will be reported as an adverse event (AE).

The data to be collected at the time of study intervention discontinuation will include the following:

- Reason for study discontinuation
- Adverse events
- Concomitant medications
- Relevant medical history, including:
 - Major and clinically relevant non-major bleeding events
 - Objectively documented pulmonary embolism (PE)
 - Objectively documented and confirmed proximal deep vein thrombosis (DVT) of the upper or lower extremities
 - Objectively documented micro-thrombosis (skin biopsy)
 - Objectively documented thrombosis of the dialysis, continuous renal replacement (CRRT) filters
 - Objectively documented arterial thrombosis (stroke, myocardial infarction, limb ischemia)

8.2 Participant Discontinuation/Withdrawal from the Study

Participants are free to withdraw from participation in the study at any time upon request. An investigator may discontinue or withdraw a participant from the study for the following reasons:

- Pregnancy
- Significant study intervention non-compliance
- If any clinical adverse event (AE), laboratory abnormality, or other medical condition or situation occurs such that continued participation in the study would not be in the best interest of the participant
- Disease progression which requires discontinuation of the study intervention
- If the participant meets an exclusion criterion (either newly developed or not previously recognized) that precludes further study participation

- Participant lost to follow-up after several attempts to contact subject to schedule study visit.

The reason for participant discontinuation or withdrawal from the study will be recorded on the Case Report Form (CRF). Subjects who sign the informed consent form and are randomized but do not receive the study intervention may be replaced. Subjects who sign the informed consent form, and are randomized and receive the study intervention, and subsequently withdraw, or are withdrawn or discontinued from the study, will not be replaced.

9. Correlative/Special Studies

For subjects who agree to participate in a research repository, we will collect 5mL of plasma for thrombin generation assays and clot lysis at certain time points (see Section 6.1 for more details). Samples will be stored in a special freezer located in [name] laboratory.

10. Measurement of Effect

10.1 Response Criteria

1. Primary objective: To determine if therapeutic anticoagulation improves 30-day mortality in COVID 19 positive patients compared to intermediate dose prophylaxis.
2. Secondary Objectives
 1. To assess if therapeutic anticoagulation reduced the length of ICU stay.
 2. To determine if therapeutic anticoagulation reduces the number of documented venous thromboembolism (VTE), arterial thrombosis (stroke, myocardial infarction other) and micro thrombosis.
 3. To evaluate if therapeutic anticoagulation leads to increase major and clinically relevant non-major bleeding events as defined by the International Society of Thrombosis and Haemostasis (ISTH) criteria.

10.2 Duration of Response

Duration of response will be evaluated according to evidence of thrombosis or bleeding events during the follow up period as defined in 10.1

10.3 Progression-Free Survival

Not applicable.

10.4 Other Response Parameters

Normalization of laboratory values including: D-dimer, prothrombin time (PT), fibrinogen, FVIII and VWF and complete blood count

11. Data Reporting / Regulatory Considerations

11.1 Data Collection

The data collection plan for this study is to utilize REDCap to capture all treatment, toxicity, efficacy, and adverse event data for all enrolled subjects.

11.1.1 REDCap

REDCap (Research Electronic Data Capture) is a free data management software system that is fully supported by the Weill-Cornell Medical Center CTSC. It is a tool for the creation of customized, secure data management systems that include Web-based data-entry forms, reporting tools, and a full array of security features including user and group based privileges, authentication using institution LDAP system, with a full audit trail of data manipulation and export procedures. REDCap is maintained on CTSC-owned servers that are backed up nightly and support encrypted (SSL-based) connections. Nationally, the software is developed, enhanced and supported through a multi-institutional consortium led by the Vanderbilt University CTSA.

The blocked randomization scheme will be incorporated into REDCap and assignments will be generated via a randomization module within REDCap.

11.2 Regulatory Considerations

11.2.1 Institutional Review Board/Ethics Committee Approval

As required by local regulations, the Investigator will ensure all legal aspects are covered, and approval of the appropriate regulatory bodies obtained, before study initiation.

Before initiation of the study at each study center, the protocol, the ICF, other written material given to the patients, and any other relevant study documentation will be submitted to the appropriate Ethics Committee. Written approval of the study and all relevant study information must be obtained before the study center can be initiated or the IP is released to the Investigator. Any necessary extensions or renewals of IRB approval must be obtained for changes to the study, such as amendments to the protocol, the ICF, or other study documentation. The written approval of the IRB together with the approved ICF must be filed in the study files.

The Investigator will report promptly to the IRB any new information that may adversely affect the safety of the patients or the conduct of the study. The Investigator will submit written summaries of the study status to the IRB as required. On completion of the study, the IRB will be notified that the study has ended.

All agreed protocol amendments will be clearly recorded on a protocol amendment form and will be signed and dated by the original protocol approving signatories. All protocol amendments will be submitted to the relevant institutional IRB for approval before implementation, as required by local regulations. The only exception will be when the

amendment is necessary to eliminate an immediate hazard to the trial participants. In this case, the necessary action will be taken first, with the relevant protocol amendment following shortly thereafter.

Once protocol amendments or consent form modifications are implemented at the lead site, Weill Cornell Medicine, updated documents will be provided to participating sites, as applicable. Weill Cornell Medicine must approve all consent form changes prior to local IRB submission.

Relevant study documentation will be submitted to the regulatory authorities of the participating countries, according to local/national requirements, for review and approval before the beginning of the study. On completion of the study, the regulatory authorities will be notified that the study has ended.

11.2.2 Ethical Conduct of the Study

The Investigators and all parties involved should conduct this study in adherence to the ethical principles based on the Declaration of Helsinki, GCP, ICH guidelines and the applicable national and local laws and regulatory requirements.

This study will be conducted under a protocol reviewed and approved by the applicable ethics committees and investigations will be undertaken by scientifically and medically qualified persons, where the benefits of the study are in proportion to the risks.

11.2.3 Informed Consent

The investigator or qualified designee must obtain documented consent according to ICH-GCP and local regulations, as applicable, from each potential subject or each subject's legally authorized representative prior to participating in the research study. Subjects who agree to participate will sign the approved informed consent form and will be provided a copy of the signed document. Given the disease state, potential participants may be sedated and/or on a ventilator; in such cases, the subject's legally authorized representative will be asked to provide informed consent on behalf of the subject. Subjects who enter the study with a legally authorized representative will be re-consented once they regain capacity to consent. Subjects who do not speak English may be consented using a translated short form in accordance with IRB requirements.

The initial ICF, any subsequent revised written ICF and any written information provided to the subject must be approved by IRB prior to use. The ICF will adhere to IRB requirements, applicable laws and regulations.

11.2.4 Compliance with Trial Registration and Results Posting Requirements

Under the terms of the Food and Drug Administration Modernization Act (FDAMA) and the Food and Drug Administration Amendments Act (FDAAA), the Sponsor-Investigator of the trial is solely responsible for determining whether the trial and its results are subject to the requirements for submission to <http://www.clinicaltrials.gov>. Information posted will allow subjects to identify potentially appropriate trials for their disease conditions and pursue participation by calling a central contact number for further information on appropriate trial locations and trial site contact information.

11.2.5 Record Retention

Essential documents are those documents that individually and collectively permit evaluation of the study and quality of the data produced. After completion of the study, all documents and data relating to the study will be kept in an orderly manner by the Investigator in a secure study file. Essential documents should be retained for 2 years after the final marketing approval in an ICH region or for at least 2 years since the discontinuation of clinical development of the IP. In addition, all subjects medical records and other source documentation will be kept for the maximum time permitted by the hospital, institution, or medical practice.

12. Statistical Considerations

12.1 Study Design/Endpoints:

Primary Endpoint:

Efficacy Outcomes

- Death at 30 days

Secondary Endpoints:

Efficacy Outcomes

1. Length of ICU stay
2. Objectively documented pulmonary embolism (PE), proximal deep vein thrombosis (DVT) of the upper or lower extremities, thrombosis of the dialysis, continuous renal replacement (CRRT) filters; micro-thrombosis (skin biopsy), arterial thrombosis (stroke, myocardial infarction, limb ischemia)
3. Major bleeding, (as per ISTH guidelines), and clinically relevant non-major bleeding events.

12.1.1 Primary Endpoint: Death at 30 days (primary)

12.1.2 Secondary Endpoint: Length of ICU stay.

12.1.3 Secondary Endpoint: Composite endpoint of:

- Objectively documented pulmonary embolism
- Objectively documented confirmed proximal deep vein thrombosis (DVT) of the upper or lower extremities.
- Objectively documented micro-thrombosis (skin biopsy).
- Objectively documented thrombosis of the dialysis, continuous renal replacement (CRRT) filters.
- Objectively documented arterial thrombosis (stroke, myocardial infarction, limb ischemia).

12.1.4 Secondary Endpoint: Safety Outcomes of major bleeding and clinically relevant non-major bleeding events defined as:

Major bleeding, defined (as per ISTH guidelines) as acute clinically overt bleeding associated with one or more of the following:

A decrease in hemoglobin of 2 g/dL or more;
A transfusion of 2 or more units of packed red cells;
Bleeding that occurs in at least one of the following critical sites:

- i. Intracranial
- ii. Intra-spinal
- iii. Intraocular (within the corpus of the eye; thus, a conjunctival bleed is not an intraocular bleed)
- iv. Pericardial
- v. Intra-articular
- vi. Intramuscular with compartment syndrome
- vii. Retroperitoneal

Bleeding that is fatal; Bleeding that necessitates surgical intervention.

Clinically relevant non-major bleeding event, defined as acute clinically overt bleeding that does not meet the criteria for major and consists of;

- a) Any bleeding compromising hemodynamics;
- b) Spontaneous hematoma larger than 25cm², or 100cm² if there was a traumatic cause;
- c) Intramuscular hematoma documented by ultrasonography;
- d) Epistaxis or gingival bleeding requiring tamponade or other medical intervention or bleeding from venipuncture for >5 minutes;
- e) Hematuria that was macroscopic and was spontaneous or lasted for more than 24 hours after invasive procedures;
- f) Hemoptysis, hematemesis, or spontaneous rectal bleeding requiring endoscopy or other medical intervention;
- g) Clinically relevant bleeding defined as the composite of major and clinically relevant non-major bleeding;
- h) Permanent early discontinuation of the anticoagulant due to safety reasons.

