12.4.2 Analysis of Secondary Endpoints

Length of ICU stay: We will compare the length of stay between arms using student's t-test. The length of time will be the total length of time in the ICU during the 30 days. This can be continuous or non-continuous time (i.e. a subject is discharged from ICU and then readmitted to ICU).

Thrombosis composite endpoint: All participants will be categorized as having developed one of the components of the composite endpoint or not through 30 days. The endpoint will be analyzed using chi-square test as described for the primary endpoint. We will also graphically display time to event. We will report the proportion of subjects in each diagnosed with each of these components. The primary analysis will censor participants who die without known thrombotic event. A supporting analysis will consider these deaths as part of the endpoint.

Safety Outcomes: All participants will be categorized as having developed a major bleeding events or a non-major clinically significant bleeding event and we will compare the proportions using chi-square test as described for the primary endpoint. We will also report major and non-major clinically significant bleeding event separately by arm.

Note: All secondary endpoint outcome proportions will be compared between the two treatment arms by the chi-square test or Fisher's exact test, as appropriate. Two-sided exact Clopper-Pearson 95% confidence intervals will be calculated for treatment arm differences, as appropriate.

All p-values will be two-sided with statistical significance evaluated at the 0.05 alpha level. Ninety-five percent confidence intervals for all parameters of interest will be calculated to assess the precision of the obtained estimates. All analyses will be performed in R Version 3.6.1 (R Foundation for Statistical Computing, Vienna, Austria). Note: The statistical considerations section was written in conjunction with the Division of Biostatistics, Department of Population Health Sciences.

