13.1 Adverse Event Definition

An adverse event (also referred to as an adverse experience) can be any unfavorable and unintended sign (e.g., an abnormal laboratory finding), symptom, or disease temporally associated with the use of a drug, and does not imply any judgment about causality. An adverse event can arise with any use of the drug (e.g., off-label use, use in combination with another drug) and with any route of administration, formulation, or dose, including an overdose.

Because this is a trial focusing on a critically ill population where adverse events are expected to occur frequently, only AEs meeting the following criteria will be collected and reported:

1. AEs related to bleeding (any major or clinically significant non-major bleeding) or thrombotic events (DVT/PE, stroke, myocardial infarction, peripheral embolism, skin thrombosis).
2. Any adverse event that results in interruption or discontinuation of the assigned anticoagulant treatment.
3. Any adverse event that meets the criteria for serious, as defined in Section 13.2.

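### The non-major bleeding list contains a stop-for-safety item that, read literally, can bring non-bleeding events into the tested bleeding endpoint, plus a circular composite item

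*Combined protocol and SAP*

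**What the plan says.** Section 12.1.4 introduces clinically relevant non-major bleeding as "defined as acute clinically overt bleeding that does not meet the criteria for major and consists of" a list of items a) to h). Items a) to f) describe bleeds. Item g) is "Clinically relevant bleeding defined as the composite of major and clinically relevant non-major bleeding". Item h) is "Permanent early discontinuation of the anticoagulant due to safety reasons". Section 1.2.5 carries the same two entries, in the same order, as items l and m.

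Section 12.4.2 sets the analysis: "All participants will be categorized as having developed a major bleeding events or a non-major clinically significant bleeding event", with the proportions compared by chi-square. It adds: "We will also report major and non-major clinically significant bleeding event separately by arm".

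Three other places bear on this:
- Section 7.9 gives a parallel bleeding list under "Subjects may discontinue therapy if any of the following events occur". It keeps the composite entry but lacks the discontinuation item, macroscopic hematuria and fatal bleeding. The same section also ends treatment for "Unacceptable adverse event(s)", with no restriction to bleeding.
- Section 13.1 collects bleeding and thrombotic events as one adverse event category and, as a separate one, "Any adverse event that results in interruption or discontinuation of the assigned anticoagulant treatment".
- Section 7.11 states that the trial is open-label.

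**The concern.** Two entries in the non-major list are not non-major bleeds.

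Item h/m is a treatment decision, and its wording covers any safety reason. Because the tested endpoint is major or non-major bleeding, anyone admitted by this item enters the chi-square comparison. Staff and patients know the assigned arm, so stopping can differ between arms for reasons other than bleeding. Even when it does not differ, it adds events unrelated to bleeding.

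Item g/l makes the definition refer to itself, and it names major bleeding inside a category that excludes major bleeding.

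What is at stake is the reading of the trial's only bleeding endpoint, secondary endpoint 3. Section 2.4.3 hopes to show that therapeutic dosing is as safe as intermediate dosing, so a distorted comparison in either direction matters.

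**Working it through.** **No figure to reproduce.** The documents state no bleeding rate, discontinuation rate or power for this endpoint. The only design calculation, in section 12.2, concerns mortality. From the documents come 93 patients per arm and the two-sided 0.05 chi-square test. Every bleeding and stopping rate below is an assumption.

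**Item g/l, by counting.** Suppose an arm has 5 patients with major and 8 other patients with only non-major bleeding.
- Combined endpoint without g: 5 + 8 = 13. With g: still 13, because major bleeds are already in it.
- Major count: 5 either way.
- Separately reported non-major count: 8 without g, 13 with g applied literally.

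So g affects one descriptive row and not the test.

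**Item h/m, two readings.**
- *Literal:* any permanent stop for safety counts, including one for a non-bleeding adverse event under section 7.9.
- *Under the lead-in:* only a stop linked to an overt bleed that is not major counts.

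A patient who stops for a non-bleeding adverse event and never bleeds is an event under the first reading and not under the second.

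**Literal reading, no true difference.** Let b be the true bleeding proportion and q the proportion with a non-bleeding safety stop and no bleed; the observed proportion is b + q. Take b = 10% in both arms. Summing the exact binomial probabilities of all outcomes in which the uncorrected chi-square exceeds 3.84, with n = 93 per arm, gives:

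| Added stops (intermediate vs therapeutic) | Observed endpoint | Significant results |
|---|---|---|
| none | 10% vs 10% | 5.1% |
| 1% vs 2% | 11% vs 12% | 5.6% |
| 2% vs 4% | 12% vs 14% | 6.9% |
| 1% vs 3% | 11% vs 13% | 7.1% |
| 2% vs 8% | 12% vs 18% | 20.6% |
| 1% vs 9% | 11% vs 19% | 33.2% |

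With equal arm sizes, swapping the arms gives the same percentages, so the table does not depend on which arm has more stops.

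**Literal reading, true difference, equal stops.** Let true bleeding be 5% vs 15% and non-bleeding stops 5% in each arm, independent of bleeding. The observed proportion is 1 − (1 − b)(1 − q):
- 1 − 0.95 × 0.95 = 9.75%
- 1 − 0.85 × 0.95 = 19.25%

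The difference falls from 10.0 to 9.5 points and the ratio from 3.0 to 1.97.

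Normal-approximation power is Φ{(|d|√n − 1.96√[2p̄(1 − p̄)]) / √[p₁(1 − p₁) + p₂(1 − p₂)]}, where d is the difference and p̄ the mean of the two proportions:
- Without stops: (0.964 − 0.832)/0.418 = 0.317, so power is 62.5%.
- With stops: (0.916 − 0.976)/0.493 = −0.121, so power is 45.2%.

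Exact enumeration gives 64.8% and 45.5%.

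**The case against.** The strongest reply is that the lead-in governs every item. Under it, h admits only stops tied to an overt non-major bleed. This is a coherent reading: an overt bleed that meets neither the major criteria nor items a) to f), but ends treatment, would fit. Section 2.4.1 calls bleeding the main side effect and section 7.7.1 links delaying or stopping doses to bleeding, so many safety stops may be bleeds in any case. For kidney injury in both arms, and for heparin-induced thrombocytopenia in the therapeutic arm, sections 3.1 and 7.7 provide a change of agent. Whether such a change is a permanent discontinuation is not stated.

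This stands in part. A reader might infer that the endpoint as written does count the wrong events; the documents support only that it can. The narrower reading does not settle the matter, because the item is worded for safety in general, section 7.9 permits stopping for non-bleeding adverse events, and nothing tells a coder which reading to use.

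A reader might also infer that the bias must run against therapeutic dosing, since clinicians may stop the higher dose more readily. The documents give no stopping rates by arm. Small imbalances barely move the error rate, and equal rates hide a real excess instead of creating a false one.

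**Conclusion.** The point holds in a limited form and should be corrected before the bleeding data are classified.

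- **Item h/m** leaves open whether non-bleeding stops count in the tested bleeding endpoint. If they do, the effect runs from negligible (5.6% significant results against 5.1%) to large (33.2%) when there is no true difference. With a true 5% vs 15%, equal 5% stops cut power from about 63–65% to about 45%. These sizes rest on assumed rates and on the literal reading.
- **Item g/l** is a misplaced definition of the composite. A reader might infer that it corrupts the bleeding comparison. It does not: the combined endpoint and the major count are unchanged, and only the separate non-major count can be inflated.

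It would also be too strong to call this the main safety endpoint. No section gives it that name: it is secondary endpoint 3, listed among efficacy outcomes in section 12.1 and as a safety outcome in section 12.1.4.

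**What to change.** 1. In sections 12.1.4 and 1.2.5, remove items g/l and h/m from the non-major list.
2. Define clinically relevant bleeding once, outside the list, as major or clinically relevant non-major bleeding. Name it in section 12.4.2 as the variable for the chi-square comparison, and keep the separate reporting of the two components.
3. Report permanent discontinuation for safety reasons as its own outcome by arm. State whether a change of agent within the assigned arm counts as discontinuation.
4. Reconcile the bleeding list in section 7.9 with sections 12.1.4 and 1.2.5. This concerns agreement between the definitions, not when treatment should stop.

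The cost is wording in four sections (1.2.5, 7.9, 12.1.4 and 12.4.2). No new data are needed: section 8.1 already records the reason for discontinuation and any bleeding events at that time, and section 13.1 already captures adverse events that lead to discontinuation.
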